### 3.1 Primary endpoints

The primary endpoint is the peripheral blood Treg% (or other immunoregulatory cells) and mRNA AR signatures seen prior to and during either successful (no rejection) vs. failed (rejection) TAC-WD/EVL.

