**Primary endpoint:**

The primary endpoint is the peripheral blood Treg% (or other immunoregulatory cells) and messenger ribonucleic acid (mRNA) acute rejection (AR) signatures seen prior to and during either successful (no rejection) vs. failed (rejection) TAC-WD/EVL.

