## 3 Objectives

**Primary Objective:** To identify cellular and genomic metrics of immune regulation that may predict successful TAC withdrawal in favor of EVL early after LT.

*It is our hypothesis that these markers of immunoregulation are more pronounced with successful (no rejection) vs. unsuccessful (rejection) TAC-WD/EVL.* The approach will be to analyze the peripheral blood for phenotypic Tregs correlating with mRNA footprints of regulation. These analyses will be performed in a prospective pilot clinical trial of LT recipients on standard combination TAC and EVL at 1 to 2 months post-LT selected to undergo TAC-WD/continued EVL at 3-4 months ( $\pm$  1 month). Thus, based on the clinical trials, we expect rejection to occur in 20% in the 1-2 month period following TAC-WD/EVL and that this will be predicted by bioassays analyzed prior to and/or immediately after full TAC-WD. Alternatively, we expect 80% to not experience rejection with TAC-WD/EVL and that this will be predicted by bioassays analyzed prior to and/or right after full TAC-WD. Therefore, the use of these assays would eventually serve to detect and predict appropriate candidates for successful early TAC-WD/EVL, enhancing the use of EVL in LT and allowing patients to be spared of CNI toxicity past the first 3-4 months following LT.

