### **10.2 Analysis of the primary objective(s)**

Primary objective: To identify cellular and molecular metrics of immune regulation that may predict successful TAC withdrawal in favor of EVL early after LT.

Overall Strategy and Rationale: The objective is to test the working hypothesis that, in a prospective study, cellular and genomic markers of immunoregulation become more pronounced after early rejection-free TAC-WD/EVL compared to failed (rejection) TAC-WD. Conversely, if these markers do not signify immunoregulation, we hypothesize that TAC-WD/EVL will not be successful (i.e. rejection will ensue requiring reinstatement of TAC). The rationale is that the immunoregulatory mechanisms of IS therapy (EVL vs. CNI) can be more adequately clarified and that a higher % of patients can undergo successful TAC-WD/EVL by utilizing these serial, safe blood biomarkers to predict rejection, before it occurs, i.e. by comparing these signals right before and after TAC-WD. Our hypothesis is based on our previous observations that late mTOR-I conversion increased % of Treg/DCreg in blood/tissue sites and generated immunoregulatory proteogenomic signatures and that AR can be diagnosed in the peripheral blood by genomic microarrays. Therefore, the plan is to perform sequential flow cytometry immunophenotyping and genomic signature analysis in the blood before, during and after attempted TAC-WD/EVL.

Studies Planned and Methods:

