i) Blood Immunophenotyping. The approach will be to conduct flow cytometry immunophenotyping of peripheral blood before TAC-WD initiation (1 to 2 months and 3 months ( $\pm$  1 month)), right at total TAC-WD (4 months ( $\pm$  1 month)), 2 weeks after full TAC-WD (4.5 months ( $\pm$  1 month)) and study end (6 months ( $\pm$  1 month)) post-LT to analyze cellular changes. Methods: The Immune Monitoring Laboratory at NU (Co-Director [name]) will perform the immunophenotyping. PBMC are isolated from heparinized 30 cc samples on Ficoll-Hypaque gradients. Surface markers are detected with monoclonal antibodies for the T cell subsets CD3, CD4, CD8, CD25, CD45RA, CTLA4 and CD127 followed by fixation/permeabilization/incubation with human FOXP3 antibodies and final flow cytometric analysis. RBC-lysed peripheral blood is also labeled with monoclonal antibodies for T cell subsets, naïve/memory/regulatory B cells (CD19, CD27, IgD, IgM, IL-6), monocytes (CD14) and NK cells (CD56) to quantify the absolute cell numbers per  $\mu$ L. In addition, dendritic cell surface markers are analyzed as follows: monocyteoid vs. plasmacytoid (CD11c; CD123) ratio; antigen processing markers (CD83; CD205); markers inducing Tregs (ILT3; ILT4). For statistical analysis, we perform within subject comparisons on PBMC for both successful and failed TAC-WD/EVL groups using appropriate paired analysis (paired t-test or Wilcoxon Signed Rank test). For the main hypothesis testing, repeated measures of analysis of variance (RM-ANOVA) are used to test the trajectory variations between the groups on PBMC over time. Two-sided F-test statistics are applied;  $\alpha=0.05$  (stats by NU Transplant Statistician).

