ii) Gene Expression Microarrays: The approach will be to conduct parallel serial genomic bioassays of peripheral blood before and after attempted TAC-WD/EVL (same time points as immunophenotyping). Methods: The Genomics Core at Scripps Clinic (Director, [name]) will perform the microarray analysis. Blood will be collected in PaxGene tubes and sent to Scripps for the gene microarrays. Affymetrix® Hu133 Plus Peg microarrays will be used to test for differentially expressed genes between those developing AR vs. without AR during TAC WD. We will also perform biological function and canonical pathway mapping of several immune/inflammatory gene pathways. For statistical analysis, we report for each mRNA and microRNA comparison the T-test p-value, its non-parametric analog (Kruskal Wallis test), the fold change, and for multi-analyte signatures, the area under the receiver operating curve (concordance index/C-index) and q-values by member genes/proteins. We then calculate the predictive accuracy, sensitivity and specificity of each signature (statistics by [name] informatics group at Scripps Clinic)

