### **10.2.1 Variable**

The main variables are the peripheral blood Treg% (or other immunoregulatory cells) and mRNA AR signatures seen prior to and during either successful (no rejection) vs. failed (rejection) TAC-WD/EVL.

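### As written, the primary analysis would score new gene signatures without validation and test flow markers mainly on a term that misses stable pre-withdrawal differences; the criterion for the endpoint being met is not stated

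*Combined protocol and SAP*

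**What the plan says.** **Endpoint.** Section 3.1 (Primary endpoints) states "The primary endpoint is the peripheral blood Treg% (or other immunoregulatory cells) and mRNA AR signatures seen prior to and during" successful or failed withdrawal. The synopsis says the same, and section 10.2.1 (Variable) repeats it: "The main variables are the peripheral blood Treg% (or other immunoregulatory cells) and mRNA AR signatures". The alternative cell types, the visit and the summary measure are not fixed.

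**Flow analysis.** In section 10.2 (i), repeated in 10.3.3, the main hypothesis test is an RM-ANOVA whose F-tests "are used to test the trajectory variations between the groups on PBMC over time". "Two-sided F-test statistics are applied" at α=0.05. The panel covers T-cell subsets including Tregs, B-cell subsets, monocytes, NK cells and several dendritic-cell markers. No adjustment across them is given.

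**Gene expression.** In section 10.2 (ii) the arrays are used "to test for differentially expressed genes between those developing AR vs. without AR during TAC WD". The plan then reports AUC for multi-analyte signatures, q-values for their member genes or proteins, and each signature's accuracy, sensitivity and specificity. It describes no validation step.

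**Aims.** Section 3 (Objectives) expects that rejection will occur and that "this will be predicted by bioassays analyzed prior to and/or immediately after full TAC-WD". The working hypothesis in section 10.2 is that "cellular and genomic markers of immunoregulation become more pronounced after early rejection-free TAC-WD/EVL" than after failed withdrawal.

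**Decision.** Section 3.3, items 1 and 2, uses met or not met to choose between two funding requests. Either the flow or the genomic part can make the endpoint met, if it is predictive in a preliminary sense. No p-value, AUC or marker rule is attached.

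**Follow-up.** The footnote to Table 7-1 and section 7.3 end the study for a patient whose rejection occurs after everolimus has been added.

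**The concern.** The pilot exists to choose the markers and time points for a larger trial. Three features work against that.

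- Selecting genes on the outcome and scoring them in the same few patients gives performance figures that look excellent whether or not there is a signal. Q-values on the member genes do not correct an AUC or a sensitivity.
- The flow test that the text describes asks whether trajectories diverge. That suits the hypothesis that markers become more pronounced after withdrawal. It does not suit prediction, where a marker that is steadily higher or lower in future rejectors before withdrawal would be just as useful.
- The reader cannot tell which result would make the endpoint met. Flow markers get no multiplicity control of any kind, although genes do.

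At stake is a wrong or missed lead for the next study, drawn from about 5 rejectors.

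**Working it through.** The plan gives no power or family-wise error figure, so there is nothing of its own to reproduce.

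**Inputs from the documents**
- Group sizes: 15 without and 5 with rejection (Figure 6 note). Section 10.4 expects 14–15 and 4–5. The 20% in section 3 gives 0.20 × 20 = 4, hence 16 vs 4.
- Four funded scheduled blood visits: months 3, 4, 4.5 and 6 (Table 7-1).
- α = 0.05 per F-test (section 10.2).

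**Assumptions (not in the documents)**
- Normal data, SD 1, within-patient correlation 0.5.
- Number of flow markers k and their correlation.
- A signature of 20 genes.

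**1. Signature selected and scored in the same patients.** Independent noise genes (100, 1,000 or 10,000), top 20 by t-test, 15 vs 5, in 400, 400 and 120 data sets.
- Same-patient AUC was at least 0.96 in all 920 data sets. Mean sensitivity and specificity were 99.6–100%.
- Leaving out one rejector and one non-rejector at a time, and reselecting genes each time, gave a mean AUC of 0.48–0.49 with SD about 0.2.
- Correlated genes reduce the optimism but do not remove it. A check with 1,000 noise genes sharing one common factor (400 data sets each) gave a mean same-patient AUC of 0.95 at between-gene correlation 0.5 and 0.81 at 0.8.

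**2. A stable difference between groups.** Take a constant difference of 1.53 SD at every visit. This is the size that a single visit detects with 80% power.
- *Group-by-time term.* It uses deviations from each patient's own mean, so a constant difference cancels. Detection was 4.9%, which is the type I error.
- *Group comparisons.* With m visits averaged, the variance of a patient mean is 0.5 + 0.5/m. The noncentrality is 1.53/√variance × √(15×5/20), where √3.75 = 1.936, on 18 df.

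| Comparison | Variance | Noncentrality | Power |
|---|---|---|---|
| One visit | 1.000 | 2.96 | 80% |
| Months 3 and 4 | 0.750 | 3.42 | 90% |
| All four visits (RM-ANOVA group term) | 0.625 | 3.75 | 94% |

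The four-visit figure assumes complete data, whereas rejectors may lack months 4.5 and 6.

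A mixed model for months 3 and 4 keeps patients with a missing visit. With 0, 1, 2 or 3 of the 5 rejectors lacking month 4, power is 90%, 89%, 87% and 86%, and type I error 4.7–4.9%. At 16 vs 4, power falls from 85% to 77%.

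**3. Flow multiplicity, only if any one flow F-test at 0.05 counted as met.** For independent markers the error is 1 − 0.95^k. The simulated range covers between-marker correlation 0.8 down to 0.

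| k | 1 − 0.95^k | Simulated, 15 vs 5 |
|---|---|---|
| 1 | 5% | 5% |
| 2 | 9.8% | 8–10% |
| 4 | 18.5% | 12–19% |
| 6 | 26.5% | 15–26% |

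**The case against.** Several stronger readings are tempting, and the documents do not support them.

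- *The plan has an 8–26% false-positive rate.* No section says that any one F-test suffices. Section 3.3 ties met to prediction of rejection, which points at least as much to the accuracy figures in 10.2 (ii). Neither k nor the marker correlations are given. The rate is undefined, not known to be high.
- *RM-ANOVA cannot see a stable difference.* This is true of one term only. The group term has about 94% power for the same difference. What stands is that the text describes trajectories, does not say that the group term counts, and that term averages in months 4.5 and 6.
- *The plan leaves open whether the signature is an old one or a new one.* Section 10.2 (ii) largely answers this by looking for differing genes in this study. The previously identified signatures in section 3.3, item 3, are comparators for diagnostic work at the time of rejection, subject to future funding. The missing validation step stands.
- *One lead flow marker must be named and α split.* In a lead-finding pilot that is a trade-off. Dendritic regulatory cells also rose in the earlier sirolimus conversion study (section 1), and missing a real signal may cost more than a false lead that would be retested.

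The overfitting result is also generic: the documents state neither the signature size nor same-patient scoring. It shows what happens if the text is followed with no validation, not that the analysts will do this.

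The exploratory label is fair and limits the severity. It does not remove the point, because the plan itself sets an α, names a main hypothesis test and acts on met or not met.

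**Conclusion.** The point holds, and it is minor.

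- *Signature.* Performance figures computed without reselecting genes would be close to uninformative with about 5 rejectors. Noise gives an AUC near 1.0, against about 0.5 with reselection. The near-1.0 figure assumes 20 genes, independent noise and same-patient scoring; it is lower with strongly correlated genes but still well above 0.5.
- *Flow test.* The group-by-time term has 5% detection for a constant 1.53 SD difference. A contrast on months 3 and 4 has 90% (15 vs 5, within-patient correlation 0.5). The RM-ANOVA group term would also serve if it were named and its missing visits handled.
- *Criterion.* Met has no stated rule and flow markers have no multiplicity control. The size of any resulting error cannot be derived from the documents.

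No patient is managed on the result, and a larger study would retest any lead.

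**What to change.** 1. **Sections 10.2 and 10.3.3, gene expression.** For any signature derived in this study, report AUC, accuracy, sensitivity and specificity from cross-validation with gene selection repeated inside each fold, plus a permutation p-value.
2. **Flow markers.** Report Benjamini-Hochberg q-values across all flow markers, in line with what is already planned for genes.
3. **Predictive contrast.** Pre-specify a group difference in patients who start withdrawal (rejection during or after withdrawal vs none), over months 3 and 4, using only samples taken before rejection. Use a mixed model with visit and group, so that patients with a missing visit stay in. Month 4 is taken at or just before tacrolimus stops, so add month 4.5 as a sensitivity analysis for the period immediately after full withdrawal. Keep the trajectory test as supporting.
4. **Section 3.3.** Define met by these results. Otherwise call the analysis descriptive and drop both α and met / not met.

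Naming one lead flow marker and splitting α are options for the sponsor, not corrections.

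**Cost.** Text changes in the synopsis and in sections 3.3, 10.2 and 10.3.3, and some extra work for both statistical groups. No extra patients or samples are needed. Precision stays poor:
- For 80% power the month 3–4 contrast needs a difference of about 1.32 SD at 15 vs 5, or 1.43 SD at 16 vs 4.
- The cross-validated AUC has a null SD of about 0.2. Roughly 0.82–0.88 is needed at one-sided 5%, and about 0.9 at 2.5%.

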### 3.2 Secondary endpoints

Clinical endpoints as correlates for the success and failure of TAC-WD/EVL will serve as clinical secondary endpoints. This will include but not be limited to the following at 6 months ( $\pm$  1 month) post-LT: liver allograft and renal function, EVL & TAC side effects, infectious/malignant complications, and patient/graft survival. At study end, all secondary endpoints will be statistically compared between those who succeed or fail TAC-WD/EVL.

The other mechanistic biomarker endpoints tested potentially in the future (unfunded exploratory objectives) will focus on comparing biopsy and peripheral blood microarray signatures at the time of a rejection biopsy, comparing these biopsy signatures in rejections that occur before and after TAC-WD, and other predictive biomarkers (miRNA, DSA, proteomic, donor specific assays- see exploratory objectives below).

The primary safety endpoints are the development of rejection with TAC-WD and any graft failure due to rejection, the latter of which is not expected to happen based on the registration studies. We expect that 20% of patients will experience rejection that is reversible with resumption of TAC +/- corticosteroids, without any graft loss, all based on the registration studies. However, if any patient experiences a graft loss due to the protocol (TAC-WD) or  $\geq 30\%$  rejection is seen, the study will be terminated due to safety concerns.

### **3.3 Exploratory objectives**

As this is a pilot exploratory study, a number of possible directions may emanate from these initial results:

1) If the immunophenotypic and/or genomic biomarkers are preliminarily predictive (primary endpoint met) of AR, we would then imminently request funding to adequately power a larger study focusing in on those specific time points and biomarkers identified from the initial pilot study. This could include expansion of our single center study or perhaps a multicenter trial utilizing the AR biomarkers identified to guide patient management - e.g. continued TAC WD/EVL in patients without serial AR signals vs. no TAC WD or TAC resumption in patients with these predictive AR signals to avoid AR. This type of personalized approach would be transformational if it could be instituted in clinical practice - to avoid CNI toxicity in those predicted not to reject and to avoid rejection in those predicted to reject with CNI withdrawal.

2) If the immunophenotypic and genomic biomarkers are not predictive (primary endpoint not met) of AR, we would then request funding for other biomarkers testing from the blood samples we collected and stored pre/during/post-TAC WD. There may be alternative biomarkers that are more predictive of AR that will need to be explored, and we will have these samples available. These would include, but not limited to, the following assays which we have experience in performing:

- i) *MicroRNA*: miRNA measures can be performed from whole blood collected at each time point using the Illumina Truseq protocol. In brief, Truseq small RNA library preparations are done on RNA from clinical samples that have been extracted using the Trizol protocol and purified using the RNEasy RNA purification method that has been standardized for small RNA preservation.
- ii) *Donor Specific Antibodies (DSA)*: The adverse effects of DSA in clinical LT have been increasing recognized as shown by recent studies linking the development of DSA to rejection episodes . Therefore, we can test for the development of DSA in the current cohort of patients at the same time points. Since estimation of DSA is expensive, we can monitor for the presence of panel reactive antibodies in the sera serially at the various time points, and only test those with high PRA for DSA. The NU Comprehensive Transplant Center Lab can perform these assays.
- iii) *Cellular and Plasma Proteomics*: Our recent studies of TAC to SRL conversion in LT had revealed protein profiling of the serum/plasma can yield important information on the

immunoregulatory status of the patients. Therefore, we will collect and store sera for future serial protein analysis (same time points), either as an antibody approach contracted out to Myriad RBM®, Austin, TX or performed at NU via a collaboration with [name] whose laboratory performs top down/bottom up proteomics (both cells and plasma) by mass spectrometry.

iv) *Donor-specific Immunoregulation.* Regulatory T cells with donor-specificity are critical in maintaining transplant immunoregulation and may be even more sensitive than immunophenotyping or proteogenomic arrays. In future studies, pending funding, the approach will be to perform the Treg-MLR, assessing both donor-specific immunoregulation and hyporesponsiveness serially before and after EVL addition and TAC-WD/EVL or at rejection as a comparator - all compared with non-specific measures collected at the same time points . For this, donor spleen/lymph nodes at organ retrieval and recipient lymph nodes (collected from the native explant liver hilum) are cryopreserved at the time of transplantation. Recipient pre-transplant cryopreserved CFSE-labeled lymph node cells or PBMC ( $1-5 \times 10^5$ ) are stimulated with cryopreserved donor or third party irradiated cells ( $1-5 \times 10^5$ ) in the presence of recipient PKH26 labeled *pre-* vs. *post-* transplant PBMC as third component modulators (as low as  $5 \times 10^2$  cell dilutions). After 7 days, standard 18-hour  $^3$ H-TdR incorporation assays and CD4 $^+$  CFSE quantitation (lymphoproliferation) are performed and the percentage inhibition calculated. The %Treg (CD4 $^+$ CD25 $^{\text{high}}$ FoxP3 $^+$  cells) are calculated in the CFSE-labeled responder population by flow cytometric analyses after gating out the PKH26 labeled modulators. RM-ANOVA is performed to test the hypothesis that recipients' EVL-influenced post-operative cells "recruit" Tregs and inhibit proliferation *in vitro* in a donor-specific manner vs. TAC-influenced cells, particularly in non-rejecting vs. rejecting subjects.

3) Finally, in either scenario, there may be interest from our group or Novartis in comparing diagnostic (not predictive) peripheral blood and biopsy genomic biomarkers at the time of AR occurring before and after TAC WD/EVL. We have already identified genomic AR signatures in blood and biopsy from our prior work (all TAC-treated recipients), which can serve as comparative data for this trial. There may be differences in AR signals in TAC-treated patients vs. those who have TAC withdrawn and are on EVL monotherapy. With additional future funding, we can perform the same mRNA as above at the time of any AR and compare rejections that occur pre- and post-TAC withdrawal. This will help identify signals that may be more specific of EVL (CNI-free) rejection to be able to clinically utilize these signals to guide diagnosis and patient management. Also, we can determine if biopsy vs. peripheral blood biomarker AR signals are similar or different, so as to ascertain if blood instead of biopsies (which are risky & costly) can be utilized for rejection diagnosis specific to EVL (CNI-free) therapy. For now, we will store blood (sera/plasma, PBMC, RNA) and biopsy tissue (RNAlater) at the time of AR if these analyses are of future interest.

## 4 Study design

Overall: Prospective, open-label pilot study comparing immunoregulatory assays in non-viremic LT patients undergoing TAC-WD/EVL. The patients will serve as their own control for assays, clinical, biochemical, and histological measures, and the groups will be divided and compared by the presence or absence of rejection before, during and after the TAC-WD/EVL phase (months 0-6 ( $\pm$  1 month)). We expect to find assay measures (primary objective) consistent with immunoregulation in patients who are successfully withdrawn from TAC compared to signs of immunoreactivity/lack of immunoregulation in those who fail TAC-WD due to rejection and require TAC reinstitution.

**Clinical Trial & Timelines (Figure 6 in Appendices):** Patients will be approached for study enrollment within six months before LT but can be enrolled up until 60 days post-LT. At transplant if possible, patients consented pre-LT will have donor spleen/lymph node cells and recipient lymph node/blood cells/sera cryopreserved. This will be collected for potential future studies of donor-specific immunoregulation and donor specific antibodies (funds not requested – see Exploratory Objectives). Post-transplant, patients will be treated as standard of care with the following protocol (no antibody induction): TAC therapy (target trough 7-10 ng/mL) +/- MPA between 1-3 g/d (Cellcept®, Myfortic® or generic alternate), corticosteroids (intravenous solumedrol 500 mg daily day 2, prednisone taper from 200 mg down to 20 mg daily at week 1, then slow taper to 5 mg daily by month 3). Patients not consent pre-LT will be approached within the first 60 days post-LT. At month 1 to 2 post-LT, study continuation criteria will be determined (see inclusion criteria). If met, EVL will be started (MPA discontinued if patient treated with this) and the EVL goal troughs will be 5-8 ng/ml and TAC 3-5 ng/ml . At 3 months ( $\pm$  1 month) post-LT, patients on stable TAC + EVL meeting continuation criteria will undergo the TAC-WD/EVL phase. TAC will be reduced by 50% of daily dose. After two weeks, if liver enzymes are stable, TAC will be reduced 50% each week and discontinued at month 4 ( $\pm$  1 month) post transplant, if criteria are met. From month 4-6 ( $\pm$  1 month), the patients will be on EVL therapy alone (trough 5-8 ng/ml) with stable prednisone 5 mg/day until study end (6 months ( $\pm$  1 month)) or rejection (expected in ~20%).

Peripheral blood bioassays will be performed pre-TAC-WD (1 to 2 months and 3 months ( $\pm$  1 month)), immediately pre-TAC-WD (4 months ( $\pm$  1 month)), 2 weeks post-TAC-WD (4.5 months ( $\pm$  1 month) post-LT), at biopsy-proven rejection in any phase of the study (before or after TAC-WD phase), and at 6 months ( $\pm$  1 month) post-LT (Timeline Figure 6). We will also store extra blood samples (funds not requested – See Exploratory Objectives). Liver biopsies for standard histology will be performed only for cause at the time of rejection and not required by the protocol – extra tissue placed in RNAlater will be collected (funds not requested). The blood biomarkers will be compared between the groups (AR vs. no AR). Additionally, the patients will be monitored as standard of care with clinical laboratory tests (CBC, liver/renal function tests, IS trough levels) for other respective secondary endpoints (hematologic, liver/renal function) every 1-2 weeks. Clinical laboratory tests for other endpoints (hyperlipidemia- lipid profiles, diabetes- HbA1C, proteinuria- urine protein/creatinine) will be performed pre-EVL addition and at 6 months ( $\pm$  1 month) post-LT, all per our standard of care. Routine clinic visits will occur per standard of care (1, 2, 3, 4 & 6 months) to monitor for side effects and document any adverse events, in addition to our research coordinators maintaining close communication with the patients. The study will be completed at 6 months ( $\pm$  1 month) post-LT, which will include final assessments of clinical and laboratory outcomes. Case report forms and electronic databases documenting all immune assay results and clinical data/outcomes will be utilized for all endpoint comparisons.

